2.2 Previous Data

Below, we summarize key relevant findings from our team’s recent research, which leads to both our interest and expertise in conducting this proposed study.

Research on Reduced Nicotine Content Cigarettes. In our recently completed trial, participants were randomly assigned to smoke either (a) NNC cigarettes (11.6 mg/cig); or b) Reduced Nicotine Content (RNC) cigarettes where the nicotine content per cigarette is progressively reduced to 0.2 mg/cig in five steps over 18 weeks. Participants were then offered the choice to either (a) quit smoking with assistance, (b) continue smoking the research cigarettes, or (c) return to their own cigarettes, and were followed up for a further 12 weeks. After controlling for the baseline measure, plasma cotinine, exhaled CO and FTND score were all significantly lower at the end of randomized phase in the RNC group as

compared to the NNC group. Measures of nicotine dependence (mean cigarettes smoked per day, Penn State Cigarette Dependence Index) were significantly lower at the end of the randomized phase in the RNC group, as compared to the NNC group ($p<0.003$), whereas measures of psychiatric problems (CES-D depression score, QIDS depression score, OASIS anxiety score and MNWS nicotine withdrawal score) showed no significant change in the RNC group as compared to the NNC group. Analyses focusing on those participants who were compliant with exclusive use of research cigarettes throughout the randomized phase of the trial (in the RNC group having a reduction in mean cotinine from 245 ng/ml at visit 4 to 8 ng/ml at visit 10), found an almost identical pattern of results to the randomized phase completer analysis.

Treatment Choice: At the end of the randomized phase all participants were given the choice of (a) quit smoking with assistance, (b) continue smoking the research cigarettes, or (c) return to their own cigarettes, before being followed up for a further 12 weeks. At the end of the treatment choice phase and the whole trial (12 weeks later), the RNC group was more likely to have quit smoking (18% [17/94] vs. 4% [4/94], $p=0.004$), based on intent-to-treat analysis including all 188 randomized participants, and validated by exhaled $\text{CO}<9\text{ppm}$. This study found that gradual switching to RNC cigarettes reduced dependence and toxicant exposure and enhanced smoking cessation. In addition, there was no evidence that gradual switching may cause harms to the mental health of smokers with mood or anxiety disorders.

Research on E-cigs. Our research on e-cigs has highlighted the important differences between different types of e-cig devices and liquids.(25) We have found that very few long term e-cig users continue to use the most popular starter “cig-a-like” brands that are approximately the same size and shape as a regular cigarette, as most either stop using e-cigs or transition to an advanced device characterized by a larger battery and a manual button.(26) Our survey studies suggested that continued use of an advanced generation e-cig device is at least partly driven by nicotine delivery (e.g., 77% switched to their current device in order to obtain a “more satisfying hit”).(26)

Both our NIH-funded Tobacco Center of Regulatory Science grant (P50-DA-036107) and our collaboration with the Virginia Commonwealth University TCORS (P50-DA-036105) have enabled us to explore new approaches for assessing the toxicity and addictive effects of electronic and tobacco cigarettes. For example, we used electron paramagnetic resonance spectroscopy (EPR) to measure free radicals in aerosols from different e-cigs, liquids, and “dry puffing”. The results demonstrated, for the first time, the production of highly oxidizing free radicals from e-cigs which may present a potential cardiopulmonary risk to e-cig users.(27) We have also undertaken laboratory studies comparing the nicotine absorption in experienced e-cig users using their own brands/liquids, with that of experienced cigarette smokers. We have published on the brain fMRI effects of the e-cigs,(28, 29) and perhaps the most significant result from these studies was the marked variability in nicotine absorption from different e-cigs, despite the fact that all were regular daily users using e-cigs with a nicotine concentration in the liquid of at least 12 mg/ml, and all used a standardized puffing protocol (30 puffs over 10 minutes). Results found some participants obtained cigarette-like nicotine absorption, others obtained almost no increase in blood nicotine level.

When we analyzed the nicotine absorption by a-priori e-cig type categorizations it was clear that cigarette smokers obtained more consistently high and rapid nicotine absorption. Users of advanced e-cigs also obtained significantly higher nicotine absorption than users of first generation or “cig-a-like” brands, who absorbed minimal nicotine. These laboratory results are consistent with our survey results, demonstrating that e-cig users are likely to gravitate toward devices with characteristics that result in more efficient and rapid nicotine absorption (such as a larger more powerful battery). Our team has also developed a new questionnaire to measure dependence on e-cigs. In a collaborative study with Yale and other TCORS on 1,009 e-cig users, the 10-item Penn State *Electronic* Cigarette Dependence Index (PSECDI) correlated +0.7 with a new e-cig version of the 22-item PROMIS Nicotine Dependence

items.(30) In addition, in a large sample of current exclusive e-cig users recruited online (n=3609), we have used the PSECDI to demonstrate that regular e-cig users are less dependent on e-cigs than they retrospectively report having been on cigarettes prior to switching.(31) Recently, we replicated a similar pattern of results based on analysis of a comparison of nicotine dependence among exclusive daily e-cig users and exclusive daily cigarette smokers identified in a nationally representative sample recruited to the Wave 1 of the PATH study.(32)

In a collaborative TCORS project, we were one of two sites in a large randomized controlled trial to examine the effects of e-cigs on toxicant exposure. Along with Virginia Commonwealth University,(33) this trial involves recruiting 520 smokers interested in reducing their smoking (not quitting) and randomizing to one of 4 conditions (a cigarette substitute, or an e-cig containing 0, 8 or 36 mg/ml nicotine liquid) including 12 visits over 9 months. The Penn State site has exceeded original recruitment targets and recruited 320 of the overall planned 520 participants in that trial. The trial includes a number of health risk measures, including NNAL (primary outcome), expired air carbon monoxide (CO), nicotine (via its metabolite cotinine in urine), biochemical and hematologic health indices such as C-reactive protein (CRP), pulmonary function (via spirometry), and biomarkers of oxidative stress (e.g. glutathione). Main outcome results are currently being analyzed.

2.3 Study Rationale

We believe that a product standard restricting the permissible nicotine content for cigarettes and other combustible products offers major potential public health benefits both by reducing cigarette uptake in future generations of young people and by reducing dependence, cigarette consumption and therefore toxicant exposure among existing smokers. However, the effects of an immediate significant drop in cigarette nicotine content needs to be studied in SMHC because of their increased dependence on nicotine and vulnerability to nicotine withdrawal. In addition, the potential impact of e-cig availability in response to a reduced nicotine standard also needs to be evaluated due to the increasingly widespread use of e-cigs and their potential health effects. We believe that by using a double-blind randomized-trial design with long term (16 weeks) access to both research cigarettes and e-cigs, and comprehensive biomarker measurement in smokers with a variety of current and recent mental disorders, we will be able to thoroughly assess the effects of switching to VLNC cigarettes in this vulnerable population in a more comprehensive manner than has previously been achieved. The outcomes of this novel project will directly inform FDA on the feasibility of a low nicotine standard for cigarettes in SMHC.

3.0 Inclusion and Exclusion Criteria

3.1 Inclusion Criteria

1. Ages of 21–70
2. Smoke ≥ 5 cigarettes per day for at least the prior 12 months
3. Smoke regular, filtered cigarettes or machine rolled cigarettes with a filter
4. Exhaled CO measurement of ≥ 6 parts per million at baseline
5. No serious cigarette smoking quit attempt or use of any FDA-approved smoking cessation medication in the prior 30 days (includes any nicotine replacement, varenicline, bupropion [used specifically as a quitting aid])
6. No plans to quit smoking within the next 3 weeks
7. History of a mental health condition like depression, anxiety, panic attacks, ADHD, schizophrenia, an eating disorder, or any other mental health condition and/or have a past history of receiving treatment, counseling or medication for a mental health condition

8. Must be willing to both switch to a different type of cigarette that may contain a different amount of nicotine and to try an e-cig to substitute for some of their cigarettes
9. Must be willing and able to respond to contacts from study staff or attend visits over the study period (not planning to move, not planning extended vacation, no planned surgeries)
10. Must meet lifetime diagnostic criteria for a current or lifetime unipolar or bipolar mood disorder (e.g. major depressive disorder, major depressive episode, manic episode, hypomanic episode, bipolar disorder), an anxiety disorder (e.g. panic disorder, obsessive-compulsive disorder, post-traumatic stress disorder, agoraphobia, social anxiety disorder, generalized anxiety disorder), a psychotic disorder (e.g. mood disorder or other psychotic disorder), or an eating disorder (e.g. anorexia or bulimia) based on the MINI-International Neuropsychiatric Interview Standard (version 7.0.2).(34)
11. Able to read and write in English
12. Able to understand and give informed consent
13. Access to a computer/smartphone with e-mail and a reliable internet connection

3.2 Exclusion Criteria

1. Women who are pregnant and/or nursing or trying to become pregnant
2. Unstable or significant medical condition in the past 3 months (e.g., recent heart attack or other serious heart condition, stroke, severe angina)
3. High blood pressure (systolic >159 mmHg or diastolic >99 mmHg during screening)
4. Respiratory diseases (e.g., exacerbations of asthma or COPD, require oxygen, require oral prednisone), kidney (e.g., dialysis) or liver disease (e.g., cirrhosis), severe immune system disorders (e.g., uncontrolled HIV/AIDS, multiple sclerosis symptoms) or any medical disorder/medication that may affect participant safety or biomarker data
5. Uncontrolled mental illness or substance abuse, or inpatient treatment for these in the past 6 months
6. Use of any non-cigarette nicotine delivery product (e.g., pipe, cigar, dip, chew, snus, hookah, e-cig, strips or sticks, IQOS) in the past 7 days at screening
7. Use of an e-cig for 5 or more days in the past 28 days or any use in the past 7 days at screening
8. Use of marijuana for non-medical use or other illegal drugs/prescription drugs for non-medical use daily/almost daily or weekly in the past 3 months per NIDA Quick Screen
9. Use of medical marijuana that is smoked (combusted) or use of recreational (illegal) THC vaping products
10. Any known allergy to propylene glycol or vegetable glycerin
11. Surgery requiring general anesthesia in the past 6 weeks
12. Unwilling to remain on one flavor of cigarette (regular or menthol) for the duration of the trial
13. Previous use of SPECTRUM research cigarettes in the past 6 months
14. Other member of household currently participating in the study
15. History of a seizure disorder or had a seizure in the past 12 months
16. Currently taking or have taken medications prescribed to prevent seizures (such as Carbamazepine or Phenobarbital). Using seizure medications for off-label use (indications other than treatment for seizures) will not be included as an exclusion, these will be assessed on a case-by-case basis

3.3 Early Withdrawal of Subjects

3.3.1 Criteria for removal from study

The PI reserves the right to remove a participant from the study for any reason, based on their discretion.

Criteria for withdrawal prior to randomization

- **Participant reports using non-cigarette nicotine products at Visit 2 AND Visit 3.**
Includes cigars, pipes, snuff, chew, hookah, electronic cigarette, marijuana, IQOS, or any other illegal smoked substance, or any other nicotine containing product.
- **Participant's total cigarette consumption includes more than 10% of non-research cigarettes at Visit 3**
- **Participant has reduced their cigarette consumption by more than 50% compared to baseline (Visit 1) cigarettes per day (CPD) at Visit 2 or Visit 3.** This does not include situations of illness or other circumstances that would interfere with the participants' normal smoking behavior.
- **Participant must have smoked a total of 25 or more cigarettes in the past 6 days at Visit 2 and Visit 3.** This does not include situations of illness or other circumstances that would interfere with the participants' normal smoking behavior.
- **Reporting a quit attempt**

These circumstances of withdrawal may be taken on a case-by-case basis and actual withdrawal of the participant will be decided by the researcher. For example, continuation in the study may be possible if the participant has acted in good faith during the study.

Criteria for general withdrawal

Participants may be discontinued by the PI at any point during the study for the following reasons:

- **Missing their randomization visit:** If a participant misses Visit 3, the participant will be considered for withdrawal from the study.
- **New pregnancy:** Participants who report a new pregnancy at any point during the study will be withdrawn. (Except Visit 7; Note: no study products will be provided to the participant at Visit 7)
- **Suicide attempt:** If at any time during the study it is discovered that a participant has made a suicide attempt, they will be withdrawn from the study.
- **Cardiovascular disease (CVD) event requiring inpatient hospitalization:** CVD typically includes MI (heart attack), PTCA (angioplasty/stenting), bypass surgery, stroke, peripheral vascular disease (arterial blockages in arms or legs leading to procedure or surgery). Less common CVD problems would be new cardiac arrhythmias (e.g., new atrial fibrillation) or new valvular disease (e.g., mitral or aortic regurgitation).
- **DVT/PE (deep vein thrombosis/pulmonary embolism, i.e., blood clots in the venous system) requiring inpatient hospitalization.**
- **Elevated blood pressure at any visit (systolic >159 mmHg or diastolic >99 mmHg).**
- **Adverse events related to e-cig use:** Adverse events will be monitored at every study visit.
- **Significant smoking rate increase compared to baseline:** A participant will be withdrawn from the study if they meet BOTH of the following criteria (any visit prior to Visit 7):
 - The average cigarette per day (CPD) increase by more than 100% from the average CPD at Visit 1
 - The average of two consecutive expired breath carbon monoxide measurements increase according to the following:
 - CO is greater than 50 ppm if CO at Visit 1 is <20 ppm.
 - CO is greater than 60 ppm if CO at Visit 1 is 20 – 34 ppm.
 - CO is greater than 70 ppm if CO at Visit 1 is 35 – 49 ppm.
 - CO is greater than 80 ppm if CO at Visit 1 is 50 – 60 ppm.

- CO is greater than 90 ppm if CO at Visit 1 is 61 – 70 ppm.
- CO is greater than 100 ppm if CO at Visit 1 is 71-80 ppm.
- CO is greater than 110 ppm if CO at Visit 1 is 81-90 ppm.
- CO is greater than 120 ppm if CO at Visit 1 is 91-100 ppm.

- **Worsening substance abuse** in which the participant is behaving inappropriately at visits or demonstrates an inability to continue with the study.
- **Any inpatient hospitalization or debilitation** in which participation in the study could be detrimental to the recovery process. This will be self-reported by the participant and will be reviewed by the site PI and medical professional to determine whether continued participation in the study is appropriate (this could include recovery from a major surgery, worsening of psychiatric symptoms, etc.).
- **Use of recreational (illegal) THC products that are vaped.**
- **Participant choice:** Participants may choose to remove themselves from the study by informing the research team verbally or in writing at any point during the study.
- **Participant behavior:** If a participant is behaving in an inappropriate or threatening manner, admits to lying about eligibility criteria, is participating in other smoking research studies that could affect the primary outcome measures, appears/admits to giving away/selling study products, consistently loses study products etc., then the PI can withdraw him/her from the study at the PI's discretion.

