ask about the number of e-cig uses, number of cigarettes smoked, and any non-study cigarettes smoked. During the first week of the online survey, participants will also be asked about nicotine withdrawal symptoms. If participants do not have a reliable cell phone and internet access they will complete the information on paper logs.

Phone Call (Week 1)

Study staff will call participants to check in on their use of the study cigarettes/e-cig, remind them to use the study products, document any adverse events, and remind them to fill out their e-cigarette and cigarette use log on paper and through the online surveys. If any data on the e-cigarette and cigarette use log online survey is missing it will be collected over the phone with the participant.

Visit 4-7 (Weeks 4, 8, 12, 16)

Participants will return their e-cig and cigarette use log, and have a comprehensive set of measures recorded according to the visit (Table 1). Measures will be completed electronically on a participant computer via REDCap or administered by a study coordinator. Participants will be given a laptop with access only to the internet and an individualized REDCap survey will be opened so they can complete direct data entry. Women of child bearing potential will be retested for pregnancy at Visits 5 and 7.

The study staff will give participants e-cig and cigarette use logs and instruct them to record daily use at each visit. All participants will be asked about their use of other nicotine/tobacco products and if they vaped/smoked any other substances other than nicotine/tobacco at each visit as this could affect the urine biomarkers collected during the study (e.g. carbon monoxide and cotinine levels). Participants will be encouraged/provided advice to substitute some of their cigarettes with their e-cigarette.

Participants will receive a 4-week supply of research cigarettes (130% of daily consumption) and e-liquid pods to last approximately 28 days until the next appointment. Participants will be asked to return all opened, unopened and empty cigarette packs and all used/unused e-liquid pods to the study center at each visit in order to monitor use.

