At Visit 7, participants will return all used and unused research cigarette packs. No more cigarettes will be given. Participants will be allowed to keep their e-cig and unused e-liquid pods until the next visit. Participants will return their e-cig and cigarette use logs. Urine samples for biomarkers will be taken. Participants will complete all biomeasures and questionnaires outlined in Table 1. Participants will be advised to quit smoking completely and provided with the quitline number and sources of free/low cost nicotine replacement therapy (NRT) (see Cigarette Smoking Cessation Tools handout document). The Surgeon General booklet will also be given (see the Consumer Surgeon General Report Booklet document). Participants will be asked about their plans to either (a) go back to their own cigarettes only (b) go back to own cigarettes but supplement with an e-cig, (c) continue using an e-cig only, or (d) quit tobacco/e-cigs completely. Participants will be compensated for completing the study visit and procedures.

A study pulmonologist was added to the study team. We will be monitoring lung function using pulmonary function testing that will be completed at Visits 4-7. Any significant worsening (10% worsening or greater) in pulmonary function will be documented as an adverse event. These adverse events will be reviewed by the Safety Monitors in a timely manner. In cases where the Safety Monitor suspects that a participant may be having a respiratory adverse event related to

the study product, a study pulmonologist will be consulted. The pulmonologist will make any needed medical recommendations and a determination regarding whether the participant is able to continue with the study. For more urgent and/or serious adverse events, the Safety Monitor and/or the study pulmonologist will be consulted and immediate medical attention will be sought if needed.

Procedures during COVID-19:

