Visits 3-5 and 7 will be completed in-person. Participants will be screened for COVID-related symptoms using a modified version of the Patient Screening Questions from the Penn State Health website. Remote Visit 6 will be completed remotely over Zoom or the telephone. Questionnaires for visits outlined in Revised Table 1 will be sent to the participant via a survey link before the in-person visit. Participants will be encouraged to complete the questionnaires 2 hours before the visit, but will have up to 24 hours to complete them after the visit. Participants will return their e-cig and cigarette use log. Biomeasures will be taken as outlined in Revised Table 1. No biomeasures will be collected at Remote Visit 6. Women of child bearing potential will be retested for pregnancy at Visits 5 and 7.

The study staff will give participants e-cig and cigarette use logs and instruct them to record daily use at each visit. All participants will be asked about their use of other nicotine/tobacco products and if they vaped/smoked any other substances other than nicotine/tobacco at each visit as this could affect the urine biomarkers collected during the study (e.g. carbon monoxide and cotinine levels). Participants will be encouraged/provided advice to substitute some of their cigarettes with their e-cigarette.

Participants will receive a 4-week supply of research cigarettes (130% of daily consumption) and e-liquid pods to last approximately 28 days until the next appointment. At Visit 5, participants will receive an 8-week supply of e-cigarettes and cigarettes due to Remote Visit 6 being a remote visit. Participants will be asked to return all opened, unopened and empty cigarette packs and all used/unused e-liquid pods to the study center at each visit in order to monitor use.

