7.4.6.3 Preparation and Dispensing

All receiving, sorting, blinding of the study products will be done in secure, locked space for unblinded research staff at Penn State Hershey.

Research cigarettes: Once the cigarettes are received, they will be blinded by the unblinded study staff with unique blind codes. At Visit 3, following

confirmation of eligibility for randomization, staff will use blind codes to dispense the cartons to participants. Staff will prepare a bag of cigarette packs that will be given to the study coordinator for the participant. The blinded researchers will not be involved in the packing and labeling of the cigarettes.

E-cigs: The pods will come pre-filled in sealed packages. They will be prepared for participants by unblinded staff and stored with unique identifiers. Unblinded staff will appropriately package kits containing two JUUL devices and a supply of pods for the participants. At Visit 3, following confirmation of eligibility for randomization, participants will be randomly assigned a kit number. The blinded researchers will not be involved in the packing and labeling of the kits.

7.4.6.4

Return or Destruction of the Test Article

Research cigarettes: Participants will be instructed to return all research cigarette packs at the next in-person visit, regardless of whether they are empty, unopened or partially used. Any unused research cigarettes that are returned from the participant at the end of the study will be destroyed on site according to the general policy for drug disposal by the Investigational Drug Pharmacy.

E-cigs: Participants will be instructed to return all used and unused e-liquid pods to the study at each in-person visit to monitor use. We will ask participants to return the e-cig to the study site at the last in person visit and we will dispose of it on-site. Any unused pods that are returned at the last in person visit will be destroyed on site according to the general policy for drug disposal by the Investigational Drug Pharmacy.

Procedures during COVID-19:

Participants will receive a pre-paid envelope at Visit 7 to return all of their unused pods and e-cig to the study site. Any unused pods and e-cigs will be destroyed on site according to the general policy for drug disposal by the Investigational Drug Pharmacy.

7.4.6.5

Prior and Concomitant Therapy

Concomitant medications will be collected at baseline and regularly throughout the trial to monitor participant health conditions.

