12.0 Sharing Results with Subjects

This study is not designed to diagnose any disease or condition. However, if during the course of conducting clinical procedures (e.g., blood pressure, pulmonary function test), a participant is found to have a result outside of clinical norms, the result will be discussed with the participant at the visit where the result is identified. This information will be written in the Critical Value Letter so that it can be shared with the participant and/or their doctor. If a woman tests positive for pregnancy, the results will be shared with the participant, they will be withdrawn from the study, and they will be advised to follow up with their doctor for prenatal medical care. Overall study results will not be shared with participants.

A Participant Randomization email will be sent to all participants who were randomized in the study. The email will state their randomization assignments for both the study cigarettes and e-cigarette/pods. They will be told if study cigarettes either contained normal nicotine or very low nicotine and if the e-cigarette pods either contained nicotine or zero nicotine.

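### The Visit 7 pregnancy exemption relies on no product being provided at that visit, yet a pregnant participant may keep her e-cig and pods for up to four more weeks

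*Combined protocol and SAP*

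**What the plan says.** **Withdrawal.** Section 3.3.1 lists a new pregnancy, reported at any time, as a reason for withdrawal. It then exempts one visit and gives the reason: "Except Visit 7; Note: no study products will be provided to the participant at Visit 7".

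**Testing.** Section 7.2 makes Visit 7 (week 16) a scheduled test visit: "Women of child bearing potential will be retested for pregnancy at Visits 5 and 7".

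**Product at Visit 7.** Under both the standard and the COVID-19 procedures in section 7.2, research cigarette packs come back at Visit 7 and no more are issued. The e-cig is treated differently: "Participants will be allowed to keep their e-cig and unused e-liquid pods until the next visit". The next visit is Visit 8, at week 20, where section 7.2 places the return of devices and pods (by pre-paid envelope under COVID-19 procedures).

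**Positive test.** Section 12.0 says: "If a woman tests positive for pregnancy, the results will be shared with the participant, they will be withdrawn from the study". The same sentence contains the advice to seek prenatal care. No visit is exempted, and section 3.3.1 is not mentioned.

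**Risk.** Section 10.0 identifies nicotine, whether from cigarettes or e-cigs, as harmful to a fetus. Section 7.4.2 shows that arms 1 and 3 receive 5% nicotine pods and arms 2 and 4 receive 0% pods.

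**The concern.** At every earlier visit a reported pregnancy is a ground for withdrawal, which ends product supply. At Visit 7 the protocol relaxes this because nothing new is dispensed. A participant's exposure, however, depends on what she has in hand as well as on what she is given that day, and the Visit 7 procedures allow her to take the device and leftover pods home. No section tells staff to collect them because of a pregnancy.

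What is at stake is participant safety: avoidable fetal exposure to study-supplied nicotine in a foreseeable, if rare, event. A lesser matter is that staff who consult only section 12.0 would withdraw a woman whom section 3.3.1 keeps in, and so could lose her from the week 20 follow-up.

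**Working it through.** No figure in the plan has to be reproduced. The check sets the provisions side by side, with some simple arithmetic on timing.

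**1. Does the reason for the exemption cover product already held?**

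| Provision | Where | Applies to |
|---|---|---|
| No product provided at Visit 7 | 3.3.1 | New dispensing only |
| Cigarette packs returned, none issued | 7.2, Visit 7 | Cigarettes |
| E-cig and unused pods may be kept | 7.2, Visit 7, standard and COVID-19 | Product in hand |
| Devices and pods returned | 7.2, Visit 8 | Product in hand, at week 20 |

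The reason is true of dispensing and of cigarettes. It does not reach the e-cig and pods, and the two rows that do reach them have no pregnancy exception.

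**2. How long can she hold the product?** Visit 7 is at week 16 and Visit 8 at week 20, so 20 − 16 = 4 weeks at most.

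**3. How much product?** Under standard procedures the last routine supply is the 4-week supply at Visit 6, and 12 + 4 = week 16. Under COVID-19 procedures: "At Visit 5, participants will receive an 8-week supply of e-cigarettes and cigarettes due to Remote Visit 6 being a remote visit". Then 8 + 8 = week 16. Both supplies are meant to run out at about Visit 7, so the leftover quantity is unknown under either procedure.

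**4. Which arms?** Arms 1 and 3 hold nicotine pods, which is 2 of 4 arms under 1:1:1:1 allocation.

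**5. Which pregnancies?** Two tests are scheduled after randomization, at weeks 8 and 16, so the exemption covers 1 of 2. The gap between them is 16 − 8 = 8 weeks. Some pregnancies in that gap would be self-reported before Visit 7 and so fall under the ordinary withdrawal rule. The documents give neither the number of women of childbearing potential nor a pregnancy rate, so no count can be derived.

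**6. What happens under each withdrawal rule, outside COVID-19 procedures?**
- *Kept in under 3.3.1:* Visit 8 is her last in-person visit. She may hold the device and pods until then. This is the gap.
- *Withdrawn under 12.0:* Visit 7 becomes her last in-person visit, and section 7.4.6.4 then asks for both: "Participants will be instructed to return all used and unused e-liquid pods to the study at each in-person visit" and "We will ask participants to return the e-cig to the study site at the last in person visit". She is largely covered.

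**7. Is the primary endpoint touched?** Urine for NNAL is collected at Visit 7 itself, and section 3.3.2 asks a participant withdrawn at a visit to complete that visit. The week 16 value is therefore available under either rule.

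**The case against.** The strongest reply is that little is broken. Section 3.3.1 is the withdrawal section and names Visit 7 expressly, while section 12.0 mentions withdrawal in passing. Everyone is already advised at Visit 7 to quit smoking and is given cessation resources, and a positive test already brings prenatal-care advice. Leftover pods may be few, and half the arms hold 0% pods. Taking the e-cig from a smoker whose research cigarettes have just stopped may send her back to her own cigarettes, which section 10.0 also names as a fetal nicotine source. The investigator can in any case act case by case.

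Much of this stands. It limits the size of the point and is why the fetal benefit can only be called plausible. It does not supply an instruction to collect the product, and general discretion does not replace one.

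Three stronger readings are tempting, and the documents do not support them:

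- *Sections 3.3.1 and 12.0 are in irreconcilable conflict.* The specific rule governs the general one, so what is missing is mainly a cross-reference.
- *The permission to keep the e-cig contradicts the device-return rule in section 7.4.6.4.* Outside COVID-19 procedures the last in-person visit is Visit 8, so the two agree. Under COVID-19 procedures section 7.4.6.4 has its own envelope rule. The general pod-return instruction in section 7.2 ("all used/unused e-liquid pods to the study center at each visit in order to monitor use") likewise gives way to the specific Visit 7 sentence.
- *The envelope return has no time limit.* Retention runs only until the next visit, and section 7.2 places the envelope return under Remote Visit 8.

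**Conclusion.** The point holds as a minor safety-wording gap. The exemption in section 3.3.1 rests on a reason that does not cover product already in hand, and following section 7.2 as written can leave a woman with a positive Visit 7 test holding study pods, with nicotine in arms 1 and 3, for up to 4 weeks. The missing cross-reference in section 12.0 is a secondary matter.

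This assumes that section 3.3.1 governs at Visit 7, and that its exemption for a reported pregnancy is meant to include one found by that visit's test. The number of women is unknown and probably small. Lower fetal exposure from collecting the product is not demonstrated. A reader might infer bias or loss of power; nothing supports that. The week 16 primary endpoint is unaffected, and at week 20 the only question is whether these few women are followed and how their product use is read.

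**What to change.** 1. **Section 7.2, Visit 7, standard and COVID-19 text.** Add that the pregnancy result is obtained before the product-retention step. Any participant, in any arm, who tests positive or reports a pregnancy at Visit 7 hands back the e-cig and all pods she has with her at that visit, and returns any remainder promptly by the existing route (drop-off or pick-up, or the pre-paid envelope).
2. **Section 12.0.** After the withdrawal statement add: except at Visit 7, see section 3.3.1. Word it so that the prenatal-care advice still applies to these women.

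**Cost.** Protocol wording only, with no new test, visit or unblinding. Collecting from every arm avoids revealing allocation. The order of Visit 7 steps becomes fixed for women of childbearing potential. A woman who gives up the e-cig may go back to her own cigarettes, so the existing quit advice must be given, and her week 20 product-use data should be flagged as following an early return.
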